**Strategies for Minimizing Overall and Differential Study Attrition:** Attrition may involve an inability to collect 18-month and 4-year survey data as well as lack of access to official arrest records due to participants moving out of the relevant jurisdiction. Attrition will be minimized by: (1) collecting information at enrollment that will assist with tracking (e.g., detailed current and secondary contact information); (2) mailing a \$10 gift card to each youth during the interim between baseline and the 18-month survey assessment and again between the 18-month and 4-year survey assessments, both as a gesture to maintain participant good will and to identify participants who have moved; (3) mailing or emailing birthday cards and annual holiday cards to participants throughout their participation in the research; (4) using monetary incentives for survey completion; (5) keeping survey assessments relatively brief (i.e., 30 minutes or less); (6) building good will with control families by providing them with cash compensation for lost time in program screening and seeking out alternative supports for youth (\$150 total—see above) and, as noted above, providing them with a list of alternative programs and a tip sheet for connecting youth with supportive adults at baseline; (7) making strong efforts to collect 18-month and 4-year survey data for all participants; and (8) searching online repositories of publicly-available criminal (i.e., adult) court records using a vendor such as LexisNexis to capture offenses potentially missed through available court records (especially at the final records collection when many participants will have reached adult status).

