Attrition will be monitored across both groups (both how many and which youth attrit) as the 18-month and 4-year survey assessments ensue, thus enabling efforts to minimize differential attrition. If, for example, proportionally more controls than treatments appear to be attriting, efforts will be adjusted to ensure that the remaining controls receive additional attention in follow-up efforts. Differential attrition can also occur when the *types* of youth who attrit from the two groups differ, making the sample less comparable than it may have been at baseline. The comparability of the types of controls/treatments that are attriting will be monitored by examining the baseline attributes (e.g., delinquent behavior) of the youth for whom survey and/or records data have been collected to ensure they remain similar on these attributes. If not, efforts will be adjusted to focus more on the subsample that is needed to make the groups more comparable. These strategies require providing a different kind of attention to some group members, which is not ideal because it could yield different kinds of respondents from the two groups at follow-up (the same problem the strategy is trying to counter). However, based on experience with prior similar studies, these strategies are expected to be required to, at most, a minimal extent. To the degree they are needed, there is expected to be a net benefit in terms of a reduced threat to the internal validity for estimates of program impact. In keeping with What Works Clearinghouse [WWC, 2011] standards for acceptable attrition, every effort will be made to achieve an overall attrition rate of no higher than 20% and a differential attrition rate of no more than 5%.

For arrest records, it also will be important to distinguish between youth who continue to reside in the relevant jurisdiction but have no arrests and those who have moved and thus have missing arrest data. To facilitate this determination, participant tracking information will be used with LexisNexis to determine the current address of the youth's consenting parent and thus whether the youth (most likely) continues to reside within the original jurisdictional area.

**Analysis:** The main study analyses will test primary and secondary hypotheses regarding effects of the opportunity to receive mentoring through the BBBSA CBM program (“program participation”) as follows:

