The multiple tests associated with primary hypotheses will be conducted using the Benjamini-Hochberg (1995) family-wise adjustment (advocated by the WWC) to control for Type I error with the false discovery rate set to .05. At 18 months, the court-related arrest outcome for the period 18 months following study enrollment will serve as the primary outcome for H1, along with the survey-based assessments of delinquent behavior and substance use for H2 and H3, respectively (i.e.,  $n = 4$  tests). At 4 years, the court-related arrest outcome for the period of 4 years following study enrollment, property- and violence-related delinquent behavior for the prior 2.5 years on the 4-year follow-up survey, and substance use for the prior 6-month period on the 4-year follow-up survey will supersede these outcomes as assessed at the 18-month follow-up for purposes of family-wise Type I error adjustment (i.e.,  $n = 4$  tests). Missing data patterns will be explored and addressed using multiple imputation (Rubin, 1987) as the assumption of ignorable missingness (i.e., missing at random) is reasonable in the context of the rich set of baseline covariate measures that will be available to model the probability of missingness. For the special case of participants with de-identified arrest data (H1), the missing indicator method will be used to accommodate missingness on baseline covariates, an approach which can be expected to yield unbiased results in the context of a randomized control trial (Groenwold et al., 2012). Analyses will adhere to prevailing sets of evidence standards, particularly those of WWC and the Society for Prevention Research (SPR, Flay et al., 2005; e.g., required tests for differential attrition), thus ensuring a high level of rigor. It should be noted that planned primary analyses will, in effect, weight each site proportional to the number of participants from that site.

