involve dichotomous measures) will be smaller; with relatively low base rates already anticipated for some outcomes (e.g., arrest), the small number of events has the potential to introduce instability/imprecision into tests of program impact (i.e., regression coefficients could be biased in both positive and negative directions; see, e.g., Peduzzi et al., 1996, and Vittinghoff & McCulloch, 2007). (Note from an earlier version of this plan, prior to the decision to pursue a longer-term follow-up via the 4-year assessment: In part, to help address this concern, we may pursue longer-term follow-up so that the cumulative rates of key events (e.g., arrest) are higher, yielding more precise and stable estimates of program impact. In this case, the later follow-ups will supersede the earlier ones as primary.)

Primary study analyses will be supplemented with sensitivity analyses to determine the robustness of the findings obtained to varying assumptions and analytic approaches. These include: 1) modeling the program impact coefficient in each analysis as a random effect; 2) use of an alternative estimator (PLEASE) in analyses involving binary outcomes because of the potential for some loss of precision when adjusting impact estimates for covariates using a standard estimation approach (Colantuoni & Rosenblum, 2015); 3) using case deletion to account for missing data on outcomes and regression models that control for all potential variables related to the probability of missingness; 4) weighting of observations based on the extent to which study youth enrolled at each site are representative of youth served by BBBSA nationally in its CBM program; 5) weighting of observations by the inverse probability of availability of follow-up survey and/or arrest records data as a check on potential bias introduced by study attrition (Kosse et al., 2016); 6) treating primary outcomes (e.g., delinquent behavior) as continuous/multi-categorical rather than binary; 7) analyses using the undifferentiated measure of involvement in delinquent behavior that was examined for potential impacts with a portion of the sample prior to determining the final measures of delinquent behavior; and 8) where the same outcome measure is available at each of the 3 times of assessment, testing for program impact on change across all 3 time points using longitudinal growth models with growth modelled to reflect change over actual time (i.e., 0, 1.5, and 4 for baseline, 18 months, and 4 years).

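### The primary imputation and both attrition sensitivity analyses assume missing at random, so none can reveal bias from outcome-dependent missingness that differs by arm

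*Combined protocol and SAP*

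**What the plan says.** In the Analysis section the primary method is multiple imputation, on the ground that "the assumption of ignorable missingness (i.e., missing at random) is reasonable in the context of the rich set of baseline covariate measures" collected. The sensitivity analyses listed later in that section are meant "to determine the robustness of the findings obtained to varying assumptions and analytic approaches". Two of them concern missing data. Item (3) is "using case deletion to account for missing data on outcomes and regression models that control for all potential variables" related to missingness. Item (5) is "weighting of observations by the inverse probability of availability of follow-up survey and/or arrest records data", described as "as a check on potential bias introduced by study attrition".

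The section on minimizing attrition sets targets of at most 20% overall and 5% differential attrition. Its list of retention measures includes "building good will with control families by providing them with cash compensation for lost time in program screening" and for seeking other supports, $150 in total. The enrollment section shows this as $50 at enrollment and $50 at each follow-up survey, for controls only. If controls drop out more, "efforts will be adjusted to ensure that the remaining controls receive additional attention in follow-up efforts". The plan recognizes that such unequal attention is not ideal because "it could yield different kinds of respondents from the two groups at follow-up", but expects little need for it.

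**The concern.** A sensitivity analysis for attrition is most useful when it varies the assumption about the youth who were not seen. Items (3) and (5) change the technique and keep the assumption: given the variables in the model, missing youth are taken to have the event as often as observed youth. The other listed items (random impact coefficient, alternative estimator, site-representativeness weights, recoded outcomes, the undifferentiated delinquency measure, growth models) do not relax it. The attrition targets, the monitoring of baseline attributes by arm and the differential-attrition tests look only at rates and measured baseline traits.

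The outcomes are arrest, delinquency and substance use over up to four years, and part of the retention effort differs by arm. If the youth lost from one arm differ in outcome from those lost from the other, in ways that baseline data do not capture, all three estimates move together. Their agreement could then be reported as robustness.

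**Working it through.** **Plan's own figure.** 1,350 youth less 20% leaves 1,080, or 270 control and 810 treatment at 3:1. For 20% vs 12.8%, a pooled two-proportion test at two-sided .05 (assumed, since the plan states no per-test level) gives 80.6% power, which matches the stated 80%. The two lowest-rate pairs give less (73.3% for 5/1.9 and 76.4% for 10/5.2). That is a separate matter, since each pair is used below simply as an observed result.

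**Do the three methods separate when missing at random fails?** A simulation used a true effect of zero, event risk about 19%, 3:1 allocation, about 20% missing and two observed covariates, with 1,000 trials of 1,350. Site and family effects were omitted. The missingness odds ratios are assumptions, as the documents give none.

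| Missingness related to the outcome | Missing, treated vs control | False rejection: imputation / case deletion / weighting | Same conclusion |
|---|---|---|---|
| Not related, given covariates | 19.6% vs 19.6% | 3.9% / 3.9% / 4.1% | 98.8% |
| Both arms, odds ratio 2 | 19.6% vs 19.6% | 4.7% / 4.8% / 4.9% | 98.4% |
| Treated only, odds ratio 2 | 21.2% vs 18.5% | 16.0% / 15.9% / 16.6% | 96.9% |
| Treated only, odds ratio 3 | 21.4% vs 17.1% | 40.9% / 40.9% / 41.8% | 93.4% |

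In the last row the differential is 21.4 − 17.1 = 4.3 points, inside the 5-point target. At odds ratio 2 in the treated only, the large-sample log odds ratios were −0.192, −0.192 and −0.195 against a truth of 0. With the relation in controls only, they were +0.195, +0.192 and +0.197. So the bias can go either way, and the methods share it.

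**How large a departure would matter?** Let 20% be missing in each arm, with missing controls like observed controls. Multiply the event odds of missing treated youth by k:

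- missing treated rate r = k·o/(1 + k·o), where o = pt/(1 − pt)
- overall treated rate t = 0.8·pt + 0.2·r
- find k such that [logit(pc) − logit(t)] / √(1/(270·pc(1 − pc)) + 1/(810·t(1 − t))) = 1.96

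For 20/12.8, o = 0.128/0.872 = 0.1468.

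- At k = 1, the log odds ratio is 0.533 and the SE 0.185, so z = 2.88.
- At k = 2.075, r = 0.3046/1.3046 = 23.3% and t = 0.1024 + 0.0467 = 14.91%. The log odds ratio is 0.355 and the SE is √(1/43.2 + 1/102.8) = 0.181, so z = 1.96.

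| Control/treated rate | Tipping k | Event rate in missing treated |
|---|---|---|
| 5/1.9 | 2.79 | 5.1% |
| 10/5.2 | 2.29 | 11.2% |
| 20/12.8 | 2.08 | 23.3% |
| 30/21.3 | 1.97 | 34.7% |

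The same formula gives 1.87 for 40/30.5 and 1.81 for 50/40.2. The values depend on the test. A risk difference with unpooled SE fixed at the unshifted rates gives 1.92, 1.97, 1.96 and 1.91 for the four tabulated rows. The log-odds-ratio version is closer to the planned models.

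**Equal shift in both arms.** With k = 2 in both arms of the 20/12.8 row, controls become 0.16 + 0.2 × 0.3333 = 22.67% and treated 0.1024 + 0.2 × 0.2270 = 14.78%. The difference is 7.9 points, against 7.2 with no shift.

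**Removing the whole effect.** For 20/12.8 this needs r = (0.20 − 0.1024)/0.2 = 48.8%, an odds multiplier of 0.953/0.1468 = 6.5.

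**The case against.** The plan states its missing-at-random assumption openly and does not claim that item (5) tests it. A reader might infer that item (5) checks nothing. That goes too far, because weighting does address attrition bias that runs through measured variables. Nor must the three methods agree: they can diverge if their models use different covariates, although such divergence would reflect model specification and would not test the assumption.

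A reader might also infer that any dependence of missingness on the outcome invalidates the result. The simulation and the equal-shift calculation show otherwise. Material bias needs a dependence that differs by arm.

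It is tempting to say that tracing effort differs by arm. The documents make extra tracing conditional on observed imbalance and expect it to be minimal; only the control-only payments are fixed. They do not show that the programme's effect would be overstated.

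The 20% loss is the planning figure and is not established for each outcome. Arrest records come from courts and go missing when families move, and address tracing and online record searches are planned to limit that. With less missing, the tipping multiplier rises. The list of sensitivity analyses is also worded as open-ended, but an analysis not written down is not pre-specified.

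These points limit the claim. What stands is that no written analysis lets missing youth differ from observed youth, arm by arm.

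**Conclusion.** The concern holds in limited form. The primary imputation and items (3) and (5) share one untestable assumption, so their agreement cannot support a claim of robustness to outcome-dependent attrition that differs by arm, a risk the plan itself raises when it discusses unequal follow-up attention. At the plan's detectable differences, significance is lost at roughly 2 to 2.8 times the event odds among missing treated youth for control rates of 5% to 30%, and slightly below 2 for the two higher rates.

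These figures are illustrative. They assume 20% missing per arm and missing controls like observed controls, and they ignore covariates, clustering and the Benjamini-Hochberg step. That step's cut-offs for four tests run from .05/4 = .0125 to .05, and a stricter cut-off tips sooner. Nothing in the documents says that such a departure will occur or in which direction. The change should be made, but the primary analysis need not be replaced.

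**What to change.** Add to the sensitivity analyses in the Analysis section a delta-adjusted (tipping-point) analysis for each of the four 4-year primary outcomes:

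- Apply odds multipliers to the imputed outcomes separately by arm, over a range stated in advance (for example 0.5 to 3, labelled as an assumption because the documents offer no basis for a range).
- Report the combinations at which that outcome's conclusion changes, holding the other three p-values at their primary-analysis values. Without that convention a Benjamini-Hochberg tipping point for a single outcome is undefined.
- Label any 18-month version post hoc, since the revision note on the first page says those analyses were already in progress.

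Reword item (5) as a check on attrition bias related to measured variables, under missing at random.

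The cost is a few lines of text and a re-run of existing imputations with an offset; no new data are needed. The downsides are extra tables and the chance that a positive result must be reported as sensitive to the missing-data assumption.

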## Appendix A: Study Timeline

## Appendix B: Flowchart for Study Enrollment, Randomization, and Data Collection
